3.1.1 Phase 1b Study Design (Part 1)

Part 1 of the study has a single-arm 6+3 design aimed at assessing the safety of the selected starting dose of AMG 820 in combination with pembrolizumab. It will be conducted in subjects with select advanced solid tumors (CRC, pancreatic cancer, NSCLC and potentially other tumor types as per eligibility criteria). If the selected starting dose is determined not tolerable following review of safety data, additional lower dose levels will be evaluated. Up to 3 cohorts will be evaluated for safety and will include at least 6 subjects per cohort, and up to 18 subjects in total. The initial cohort will treat subjects at the selected starting dose of 1400 mg AMG 820 plus 200 mg pembrolizumab Q3W. The period for evaluation of a DLT in cycle 1 is 21 days. A

subject is not DLT-evaluable if he/she drops out before completion of cycle 1 for reasons other than an adverse event related to study drug.

- If 0 or 1 of the initial 6 evaluable subjects experience a dose-limiting toxicity (DLT) then the dose combination will be determined to be tolerable and Part 2 initiated.
- If 2 of the initial 6 evaluable subjects experience a DLT then 3 additional evaluable subjects will be enrolled.
- If 3 or more of the evaluable subjects experience a DLT (eg, 33% or higher with 9 evaluable subjects) then the dose combination will be determined to be non-tolerable and a second Part 1 cohort will be enrolled to test a decreased dose of AMG 820 in combination with 200 mg pembrolizumab. Further degree of dose modification and/or schedule of administration will be decided based on analysis of emerging safety and PK data.

Prior to opening a subsequent cohort for enrollment, the Dose Level Review Team (DLRT) will evaluate data from subjects enrolled into prior cohorts (at least 21 days of safety follow-up) including events with a longer onset time or events following exposure to multiple doses. If late onset events occur during a cohort, the DLRT may adaptively re-consider the doses evaluated within a cohort for subsequent dosing and/or possibly trigger a de-escalation or withholding of additional doses in subsequent cohorts.

3.1.2 Phase 2 Study Design

The primary objective of study Part 2 is to further evaluate safety and efficacy of the combination dose in the 4 selected CRC, pancreatic cancer and NSCLC subject groups. Other tumor types may be explored based on emerging data. The dose or doses to be evaluated in Part 2 will be based on results from Part 1. Part 2 will begin after safety of the dose level(s) explored in Part 1 has been assessed and determined to be safe.

Part 2 will include 6-9 subjects from Part 1 who have been treated with the recommended combination dose, and will enroll additional CRC, pancreatic cancer and NSCLC subjects following a Simon two-stage design: stage 1 will enroll up to 67 subjects overall, stage 2 may add another 118 subjects as per the rules described below. The recommendations to enroll stage 2 are based on ORR (see rules described below); nonetheless, the DLRT (see [Section 6.2.1.2.1](#)) will make decisions after reviewing all available safety, efficacy, pharmacokinetic and pharmacodynamic data. Analysis of data in Part 2 will be done separately for each group (Group 1, 2, 3, 4a, 4b).

- Group 1 will enroll up to 43 advanced MMR-proficient CRC subjects who are naïve to anti-PD-1/PD-L1/CSF-1/CSF-1R therapies. Eighteen (18) subjects will be enrolled during the first stage and treated with the AMG 820 plus pembrolizumab combination. If 2 or fewer subjects have an objective response per irRECIST then,

depending on the review of all available data, further enrollment may be discontinued; otherwise, enrollment up to 43 subjects will occur.

- Group 2 will enroll up to 29 advanced pancreatic cancer subjects who are naïve to anti-PD-1/PD-L1/CSF-1/CSF-1R therapies. Ten (10) subjects will be enrolled during the first stage and treated with the AMG 820 plus pembrolizumab combination. If no subjects have an objective response per irRECIST then, depending on the review of all available data, further enrollment may be discontinued; otherwise, enrollment up to 29 subjects will occur.
- Group 3 will enroll up to 55 advanced NSCLC subjects with low (< 50%) tumor PD-L1- expression who are naïve to anti-PD-1/PD-L1/CSF-1/CSF-1R agents. Nineteen (19) subjects will be enrolled during the first stage and treated with the AMG 820 plus pembrolizumab combination. If 3 or fewer subjects have an objective response per irRECIST then, depending on the review of all available data, further enrollment may be discontinued; otherwise, enrollment up to 55 subjects will occur.
- Group 4 will enroll up to 58 NSCLC subjects who have not responded to or have relapsed during monotherapy with anti-PD-1/PD-L1 agents and are anti-CSF-1/CSF-1R naïve. These subjects will be further distributed equally between two sub-groups (4a and 4b) depending on the PD-L1 expression in the tumor tissue: high ($\geq 50\%$) and low (< 50%) expression (up to 29 in each sub-group). For each sub-group, an initial set of 10 subjects will be enrolled during the first stage and treated with the AMG 820 plus pembrolizumab combination. If no subjects have an objective response per irRECIST for either subgroup then, depending on the review of all available data, further enrollment may be discontinued; otherwise, enrollment up to 58 subjects will occur.

The overall study design is described by a [study schema](#) at the end of the [protocol synopsis](#) section and [Figure 1](#) above.

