- Group 2 will enroll up to 29 advanced pancreatic cancer subjects who are naïve to anti-PD-1/PD-L1/CSF-1/CSF-1R therapies. Ten (10) subjects will be enrolled during the first stage and treated with the AMG 820 plus pembrolizumab combination. If no subjects have an objective response per irRECIST then further enrollment may be discontinued; otherwise, enrollment up to 29 subjects will occur.
- Group 3 will enroll up to 55 advanced NSCLC subjects with low (< 50%) tumor PD-L1- expression who are naïve to anti-PD-1/PD-L1/CSF-1/CSF-1R agents. Nineteen (19) subjects will be enrolled first during the first stage and treated with the AMG 820 plus pembrolizumab combination. If 3 or fewer subjects have an objective response per irRECIST then further enrollment may be discontinued; otherwise, enrollment up to 55 subjects will occur.
- Group 4 will enroll up to 58 NSCLC subjects who have not responded to or have relapsed during monotherapy with anti-PD-1/PD-L1 agents, and are anti-CSF-1/CSF-1R naïve. These subjects will be further distributed equally between two sub-groups (4a and 4b) depending on the PD-L1 expression in the tumor tissue: high ($\geq 50\%$) and low (< 50%) expression. Ten (10) subjects per subgroup will be enrolled first, during the first stage. If no objective response per irRECIST is seen in either of the subgroups then further enrollment may be discontinued; otherwise, enrollment up to 58 subjects will occur.

Sample Size:

It is anticipated that 67 to 197 subjects will be enrolled overall in this study.

Part 1 will enroll 6 to 18 evaluable subjects. The sample size in Part 1 is based on practical consideration, and it is consistent with conventional oncology studies with the objective to evaluate the safety and tolerability of a treatment combination. With 6 subjects in a cohort, there is a 47-91% probability of observing at least one DLT if the true DLT rate is 10-33%.

Part 2 evaluation of efficacy will include at least 6 subjects from part 1 who have been treated with the recommended combination dose, and will enroll additional subjects with CRC, pancreatic cancer and NSCLC up to a maximum of 185 subjects overall. The sample size in each group evaluated in Part 2 is chosen to test whether AMG 820 can enhance the anti-tumor activity observed historically with pembrolizumab alone and/or overcome lack of response to pembrolizumab monotherapy. Other indications may be included dependent on emerging data.

Summary of Subject Eligibility Criteria:

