Group 4 will consist of up to 58 NSCLC who received prior treatment with a PD-1/PD-L1 inhibitor, and failed to respond to or relapsed during therapy. These subjects must be also naive to anti-CSF-1/CSF-1R agents. There will be two sub-groups. Sub-group 4a will enroll up to 29 (only 10 enrolled initially in the first stage) subjects who have tumor PD-L1 expression <50% (see [Garon et al., 2015](#)) while sub-group 4b will enroll up to 29 subjects who have tumor PD-L1 expression \geq 50% (only 10 enrolled initially in the first stage). It is anticipated that the combination treatment of AMG 820 and pembrolizumab will have an ORR of 20% or higher in these NSCLC subjects; an ORR of 5% or less is considered to be insufficient anti-tumor activity to warrant future research. If none of the initial 10 subjects in a sub-group have an objective response then the recommendation is for enrollment to the sub-group be stopped for futility. If 4 or more of the 29 subjects in the sub-group have an objective response then the true ORR is determined to be >5%. This Simon Two-Stage design provides 80% power when the true ORR is 20% while maintaining a 1-sided, 5% alpha error when the true ORR is 5% or lower.

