10.3 Planned Analyses

10.3.1 Interim Analyses

Safety and all clinical data will be monitored on an ongoing basis. All available cumulative data will be reviewed in Part 1 by cohort, prior to making dose escalation decisions, by the Dose Level Review Team (DLRT, see [Section 6.2.1.2](#)). In study Part 2

stage 1, similar assessments will be held after each set of 20 subjects have enrolled through the end of Part 2 stage 1 enrollment.

In Part 2, a Simon Two-Stage design is used for all groups (Group 1-3, 4a, 4b) with the first stage enrolling n=18, 10, 19, 10 and 10 subjects, respectively (see [design schema](#)). Each group will enroll subjects to a first stage. The second stage for each group will be enrolled depending on clinical activity from stage 1, evaluated when the subjects have been treated for at least 6 months or earlier if the required number of responders have been reached (see [Section 10.2](#) for details). The pre-planned recommendations for enrollment to stage 2 are based on ORR per local irRECIST, however the DLRT will make the decisions for stage 2 enrollment after reviewing all available safety, efficacy, pharmacokinetic and pharmacodynamic data.

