- Group 3 will enroll up to 55 advanced NSCLC subjects with low (<50%) tumor PD-L1- expression who are naïve to anti-PD-1/PD-L1/CSF-1/CSF-1R agents. Nineteen (19) subjects will be enrolled during the first stage and treated with the AMG 820 plus pembrolizumab combination. If 3 or fewer subjects have an objective response per irRECIST then, depending on the review of all available data, further enrollment may be discontinued; otherwise, enrollment up to 55 subjects will occur.
- Group 4 will enroll up to 58 NSCLC subjects who have not responded to or have relapsed during monotherapy with anti-PD-1/PD-L1 agents and are anti-CSF-1/CSF-1R naïve. These subjects will be further distributed equally between two sub-groups (4a and 4b) depending on the PD-L1 expression in the tumor tissue: high ( $\geq 50\%$ ) and low (<50%) expression (up to 29 in each sub-group). For each sub-group, an initial set of 10 subjects will be enrolled during the first stage and treated with the AMG 820 plus pembrolizumab combination. If no subjects have an objective response per irRECIST for either subgroup then, depending on the review of all available data, further enrollment may be discontinued; otherwise, enrollment up to 58 subjects will occur.

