Group 4 will consist of up to 58 NSCLC who received prior treatment with a PD-1/PD-L1 inhibitor, and failed to respond to or relapsed during therapy. These subjects must be also naive to anti-CSF-1/CSF-1R agents. There will be two sub-groups. Sub-group 4a will enroll up to 29 (only 10 enrolled initially in the first stage) subjects who have tumor PD-L1 expression <50% (see [Garon et al, 2015](#)) while sub-group 4b will enroll up to 29 subjects who have tumor PD-L1 expression  $\geq$ 50% (only 10 enrolled initially in the first stage). It is anticipated that the combination treatment of AMG 820 and pembrolizumab will have an ORR of 20% or higher in these NSCLC subjects; an ORR of 5% or less is considered to be insufficient anti-tumor activity to warrant future research. If none of the initial 10 subjects in a sub-group have an objective response then the recommendation is for enrollment to the sub-group be stopped for futility. If 4 or more of the 29 subjects in

the sub-group have an objective response then the true ORR is determined to be > 5%. This Simon Two-Stage design provides 80% power when the true ORR is 20% while maintaining a 1-sided, 5% alpha error when the true ORR is 5% or lower.

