## **8. Interim Analysis and Early Stopping Guidelines**

### **8.1 Interim Analysis**

Safety and all clinical data will be monitored on an ongoing basis. All available cumulative data will be reviewed in Part 1 by cohort, prior to making dose escalation decisions, by the Dose Level Review Team (DLRT). In study Part 2 stage 1, similar assessments will be held after each set of 20 subjects have enrolled through the end of Part 2 stage 1 enrollment.

In Part 2, a Simon Two-Stage design is used for all groups (Group 1, 2, 3, 4a, 4b) with the first stage enrolling n=18, 10, 19, 10 and 10 subjects, respectively (see [Figure 1](#) of Study Schema). Each group will enroll subjects to a first stage. The second stage for

each group will be enrolled depending on clinical activity from stage 1, evaluated when the subjects have been treated for at least 6 months or earlier if the required number of responders have been reached. The pre-planned recommendations for enrollment to stage 2 are based on ORR per local irRECIST, however the DLRT will make the decisions for stage 2 enrollment after reviewing all available safety, efficacy, pharmacokinetic and pharmacodynamic data.

The study may be discontinued or modified at any time due to documented safety findings.

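### The Group 4 stage 2 rule is written jointly for 4a and 4b in three places but per sub-group in Protocol 10.2 and SAP 3.2, and only the per-sub-group rule has the stated Simon properties

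*Protocol*

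**What the plan says.** Group 4 (NSCLC after anti-PD-1/PD-L1 failure) is split by PD-L1 expression into 4a and 4b. Each has 10 subjects in stage 1 and at most 29 overall, so 58 together.

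**Joint wording, three places**
- Protocol 3.1.2: "If no subjects have an objective response per irRECIST for either subgroup then, depending on the review of all available data", further enrolment may be discontinued; otherwise the ceiling is 58.
- Protocol Synopsis, Study Design: "If no objective response per irRECIST is seen in either of the subgroups then further enrollment may be discontinued", with the same alternative.
- SAP 3.1.2 repeats Protocol 3.1.2 and ends "otherwise, enrollment up to 58 subjects will occur".

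**Per-sub-group wording**
- Protocol 10.2: "If none of the initial 10 subjects in a sub-group have an objective response then the recommendation is for enrollment to the sub-group be stopped".
- SAP 3.2 has the same condition: "If none of the initial 10 subjects in a sub-group have an objective response".
- Protocol 10.3.1, which points to 10.2 for details, says "a Simon Two-Stage design is used for all groups (Group 1-3, 4a, 4b". SAP 8.1 says "a Simon Two-Stage design is used for all groups (Group 1, 2, 3, 4a, 4b". Both count 4a and 4b as separate designs.

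The operating characteristics (1-sided 5% alpha at a 5% response rate, 80% power at 20%) are stated only beside the per-sub-group rule. All versions are advisory. Protocol 10.3.1 adds: "however the DLRT will make the decisions for stage 2 enrollment after reviewing all available safety".

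**The concern.** The joint sentence has one condition covering both sub-groups and one continuation number, 58. Its natural reading is that stopping is recommended only when neither sub-group has a response, and that otherwise both continue. It can also be read as stopping both when at least one sub-group has none, or distributively, one sub-group at a time. Only the distributive reading matches Protocol 10.2, and the single figure of 58 fits it poorly.

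The conflict shows when exactly one sub-group has 0/10. Protocol 10.2 then recommends stopping that sub-group, so Group 4 can reach at most 10 + 29 = 39. The natural joint reading points to 58, and the at-least-one reading stops both at 20. Two of the five efficacy groups depend on this recommendation. The stakes are lost futility stopping for an inactive sub-group on the natural reading, or stopping an active sub-group because of the other one on the at-least-one reading.

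**Working it through.** **Inputs** (Protocol 10.2 and SAP 3.2): stage 1 n = 10, futility bound 0/10, maximum n = 29 (19 in stage 2), success at 4 or more of 29, null response rate 5%, target 20%. Two assumptions are added: the sub-groups are independent, and the written recommendation is followed. Below, X10, X19 and X29 are binomial response counts in 10, 19 and 29 subjects.

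**1. Reproduce the stated design.** The probability of declaring success under the per-sub-group rule is

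P(X29 ≥ 4) − P(X10 = 0) × P(X19 ≥ 4).

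- At 5%: P(X10 = 0) = 0.95^10 = 0.5987, so alpha = 0.05475 − 0.5987 × 0.01324 = 0.0468.
- At 20%: P(X10 = 0) = 0.80^10 = 0.1074, so power = 0.8596 − 0.1074 × 0.5449 = 0.8011.

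The stated 5% and 80% are therefore those of the per-sub-group rule. With no futility stop at all, alpha is 0.0548 and power 0.8596.

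**2. How often the wordings disagree.** Either joint reading departs from 10.2 when exactly one sub-group has 0/10:

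- both 5%: 2 × 0.5987 × 0.4013 = 0.481
- 5% and 20%: 0.5987 × 0.8926 + 0.4013 × 0.1074 = 0.578
- both 20%: 2 × 0.1074 × 0.8926 = 0.192

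**3. Natural joint reading (stop only if both have 0/10).** The early-stop probability of a 5% sub-group falls from 0.599 to 0.5987² = 0.358 if the other is at 5%, or to 0.5987 × 0.1074 = 0.064 if the other is at 20%.

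Expected Group 4 size is 20 + 38 × (1 − P(both 0/10)) on this reading, against 20 + 19 × (sum of the two probabilities of at least one response) under 10.2:

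| True response rates | Rule in 10.2 | Natural joint reading | Difference |
|---|---|---|---|
| 5% and 5% | 35.2 | 44.4 | 9.1 |
| 5% and 20% | 44.6 | 55.6 | 11.0 |
| 20% and 20% | 53.9 | 57.6 | 3.6 |

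The success probability is the per-sub-group value plus P(X10 = 0) × P(X19 ≥ 4) × P(other has at least one response):

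- Alpha: 0.0468 + 0.0079 × 0.4013 = 0.0500 (other at 5%); 0.0468 + 0.0079 × 0.8926 = 0.0539 (other at 20%).
- Power: 0.8011 + 0.0585 × 0.4013 = 0.8246 (other at 5%); 0.8011 + 0.0585 × 0.8926 = 0.8533 (other at 20%).

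**4. At-least-one reading (stop both if at least one has 0/10).** Power for a 20% sub-group is 0.8011 × P(other has at least one response):

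- other at 5%: 0.8011 × 0.4013 = 0.3215
- other at 20%: 0.8011 × 0.8926 = 0.7151

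**The case against.** The best defence is that the documents already settle the matter. Protocol 10.2 and SAP 3.2 are explicit, and both also say that any group or sub-group may stop early for insufficient activity. Protocol 10.3.1 and SAP 8.1 list 4a and 4b separately, and Part 2 is analysed separately by group. Protocol 3.1.2 introduces its sentence with per-sub-group sizes, so a distributive reading is possible, and 39 lies within a ceiling of 58. The three joint sentences are in effect one sentence carried forward.

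Much of this stands: the documents lean towards the per-sub-group rule. But the three design sentences do not state it, and their only alternative to stopping is enrolment up to 58. The protocol also says that no charter will be used for the dose level review meetings and that decisions must be unanimous, so the protocol text is where the team must find its rule.

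Two further points are correct and limit the finding. First, the recommendation is advisory, and overriding it every time would move alpha to 5.5% and power to 86.0%, more than the natural reading does. Second, the 32% power figure needs the least natural reading, so little weight should rest on it.

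Finally, the Amendment 2 rationale says the sponsor has decided to stop investigating the combination. New wording may therefore change no future enrolment. Reporting which rule was used keeps its value, because the SAP covers the final analysis.

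**Conclusion.** The concern holds. The documents contain conflicting pre-planned recommendations for Group 4, and strictly only the per-sub-group rule keeps both stated properties: the natural joint reading takes alpha to 5.0% or 5.4%, and the at-least-one reading takes power below 80%.

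On the natural reading the practical loss is futility protection, and the cost in expected enrolment is smallest when both sub-groups are active. The alpha change is slight and power does not suffer, so the final inference is not invalidated. This should be fixed but is not a fatal flaw. The figures assume independent sub-groups, true response rates equal to the protocol's own null and target, and a DLRT that follows the written recommendation.

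**What to change.** In the Protocol Synopsis, Protocol 3.1.2 and SAP 3.1.2, replace the Group 4 sentence with the rule of Protocol 10.2. It should say that 4a and 4b are judged separately; that 0 responders per irRECIST among a sub-group's first 10 subjects leads to a recommendation to stop that sub-group for futility; that otherwise that sub-group may go on to 29; and that the DLRT decides after reviewing all available data. The study schema and Figure 1 are not visible in the text reviewed and should be changed too if they carry the joint wording.

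If Group 4 stage 2 decisions have already been made, the study report should state which rule was applied and the stage 1 response count in each sub-group.

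The cost is wording in three sentences plus any matching figure text. No patients are added and the Simon design in 10.2 is unchanged. Against the natural joint reading, expected enrolment falls by the differences tabulated above.

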3.2 Number of Sites

The study will be conducted at approximately 15 sites in Australia, Canada, the United States, and Europe. Additional sites and countries may be added.

Sites that do not enroll subjects within 4 months of site initiation may be closed.

3.3 Number of Subjects

Participants in this clinical investigation shall be referred to as “subjects”.

Overall, this study may enroll between 67 and 197 subjects. Six (6) to eighteen (18) subjects will be enrolled in part 1. Once the safety of the recommended dose of the combination is established in Study Part 1, stage 1 of Study Part 2 will expand enrollment up to 67 subjects (including 6-9 subjects from Part 1 who have been treated with the recommended combination dose). The subsequent stage 2 of part 2 may add another 118 subjects as per the study design rules.

Refer to [Section 10.2](#) for sample size considerations.

3.4 Replacement of Subjects

Subjects enrolled may be replaced if they are not evaluable for DLT (eg, a subject did not receive study treatment, or ended the study treatment before completion of DLT evaluation period for a reason other than experiencing a DLT).

3.5 Estimated Study Duration

3.5.1 Study Duration for Subjects

The duration of screening for each subject will be approximately 28 days. The duration of treatment will vary for each subject. Subjects enrolled in Part 1 and 2 of the study can be treated for up to 24 months if treatment is tolerable and clinical benefit is observed. All subjects will complete a safety follow-up visit approximately 135 (+7) days after the last dose of study treatment. After the safety follow-up visit, depending on the duration of their treatment on the study, some subjects will enter the long-term follow-up. The goal of the long-term follow-up is to obtain disease progression and survival information for a period of 12 months after the first combination dose. The actual duration of the study for an individual subject is dependent upon the time required to assess PFS and OS at 12 months.

For subjects who continue treatment past 12 months and up to 24 months (if tolerable and clinical benefit is observed), only Visit Date, IP Administration, and AE/SAE information will be collected in EDC. Remaining follow-up to be performed per institutional standard of care.

